1.0 PROTOCOL SUMMARY

| Clinical Investigation Title | BEACH Trial: Bovine Early Access, Compatibility, and Hemostasis Trial Study to Evaluate the Safety and Effectiveness of Early Access in Patients Who Require an Arteriovenous Conduit for Hemodialysis using the Artegraft [®] Collagen Vascular Graft [™] |
|---------------------------------|--|
| Short Title | Bovine Early Access, Compatibility, and Hemostasis (BEACH) Trial |
| Investigational Device | Artegraft® Collagen Vascular Graft™ (Artegraft) |
| Intended Use | The intended use and design of the Artegraft is unchanged. The following paragraph is from the Artegraft IFU: "The Artegraft is intended for use distal to the aorta as a segmental arterial replacement, as an arterial bypass, as an arteriovenous shunt where more conventional methods have proven inadequate, or as an arterial patch graft." |
| Study Objective | The objective of the BEACH Trial is to demonstrate that early access of Artegraft is associated with acceptable rates of successful early access, and acceptable rates of a composite of adverse events, to support a modification of existing device labeling stating that Artegraft is capable of cannulation within 72 hours post implantation. |
| Study Population | Patients with end-stage renal disease (ESRD) who require hemodialysis and are suitable for an arteriovenous graft (AVG) for hemodialysis. |
| Study Design | Prospective, multi-center randomized, open-label, treatment trial Eligible patients will be implanted with the Artegraft. After successful implant, Patients will be randomly assigned in a 2:1 ratio to early access [within 72 hours post implantation] or late access [>/= 10 days], of the Artegraft device. Day 0 is the date of first successful cannulation of the Artegraft for each patient. Patients with early access will be followed for 6 months post implantation. Patients with late access will be followed to at least 30 days after first access [30 days post Day 0]. The late access group will also be assessed for patency at 6 months through a telephone interview or office visit to provide a more robust data set. |
| Patient Number | A total of 50 patients will be randomized to early access, successfully provided early cannulation within 72 hours, and will be followed to 6 months, to provide the data required for submission to the FDA. A 12month assessment for unexpected complications will also be obtained for early access subjects. Patients randomized to the early access group who are not cannulated in the <72-hour period will be followed as a late-access subject |

Artegraft, Inc.
Protocol: ARTCT.BEACH.001

Version 4.0 CONFIDENTIAL 21June2019 Page 9 of 81

| | for 30 days after first cannulation. It is estimated that up to 10 additional patients may fall into this category. A total of 25 patients will be randomized to late access, cannulated at 10 days or later after implant and followed for at least 30 days after first cannulation [Day 0] to assess perioperative major adverse clinical events (MACE) rates and patency data. The late access group will also be assessed for patency at 6 months through a telephone interview or office visit to provide a more robust data set |
|---|---|
| Intervention Description | Patients will be implanted with the Artegraft, for vascular cannulation for hemodialysis, using standard vascular techniques, according to the Instructions for Use. |
| Number of Investigators and Study Centers | Up to five (5) investigational sites are expected to participate in the trial. |
| Study Duration | The enrollment goal is ≥3 patients per site, per month. The anticipated enrollment period is 6 months; the patient enrollment duration for early-access patients is a minimum of 6 months, and total study duration is expected to be 12 months. |
| | The follow-up period on the early access patients will be 6 months and 30 days on the late access patients. In addition, a follow-up telephone call, based on a questionnaire, will be made to the early access patients and/or dialysis centers to determine if any unexpected complications had occurred during the 6-12-month period. For this reason, all patients will be consented to 12 months. The late access group will also be assessed for patency at 6 months through a telephone interview or office visit to provide a more robust data set. |
| Primary Effectiveness Endpoint | Early access success, defined by three cannulations, the first one started within 72 hours after implantation, all with minimum dialysis flow rates of 250 ml/min pump flow rate, with a minimum 17-gauge needle. |

| Inclusion Criteria | Male or Female, 18 years or older Diagnosis of End Stage Renal Disease (ESRD) and require vascular cannulation for hemodialysis Native [autogenous tissue] AV fistula creation or cannulation is not indicated or non-viable [disadvantaged veins] Requiring repair of an existing fistula or conduit, but only if using Artegraft as an interposition placement and the Artegraft is cannulated [not the fistula]. Graft must be placed in a fresh subcutaneous tunnel. Thigh loop grafts will not be used. Able to accommodate vascular graft placement in the upper extremity (i.e., forearm, or upper arm) Capable of giving signed informed consent, which includes compliance with the requirements and restrictions listed in the informed consent form (ICF) | | | |
| | 7. Able and willing to comply with the study protocol | | | |

- 8. Agrees to initiate and maintain hemodialysis treatments
- 9. Life expectancy is > 1 year based on physician assessment

Exclusion Criteria

Patients are excluded from the trial if any of the following criteria apply:

- 1. High grade central venous stenosis/occlusion
- 2. Breast-feeding, pregnant or planning pregnancy within next 12 months.
- 3. Non-resolved infected existing grafts
- 4. Documented sepsis/bacteremia by blood culture within 4 weeks of implantation.
- 5. History of non-controlled immunodeficiency syndrome, including AIDS/HIV; Active clinically significant immune-mediated disease, not controlled by low-dose maintenance immunosuppression. The diagnosis of HIV alone, provided adequately treated, is not a contraindication for enrollment.
- 6. Severe liver dysfunction and/or coagulation or bleeding disorders.
- 7. Elevated platelet count > 1 million cells/mm3
- 8. History of heparin-induced thrombocytopenia syndrome (HIT)
- 9. Documented hypercoagulable state
- 10. Currently participating in another investigational drug or device study which may clinically interfere with any endpoints of this trial
- 11. Known hypersensitivity or contraindication to device materials or procedural medications that cannot be adequately managed medically
- 12. History or evidence of severe cardiac disease (NYHA Functional Class III or IV), myocardial infarction within 6 months of enrollment, ventricular tachyarrhythmias requiring continuing treatment, or unstable angina, uncontrolled CHF
- 13. History or evidence of severe peripheral arterial disease in the extremity selected for implant (i.e. arterial inflow insufficient to support hemodialysis)
- 14. History of cancer with active disease or treatment within the previous year, except for non-invasive basal or squamous cell carcinoma of the skin
- 15. Bleeding diathesis, other than that associated with ESRD
- 16. Scheduled renal transplant within 6 months
- 17. Patients who require chronic anticoagulation except for antiplatelet therapy. Patients currently receiving or who have received within the last month direct thrombin inhibitors, factor Xa inhibitors, or vitamin K antagonists should not be included in the study.

Artegraft, Inc.
Protocol: ARTCT.BEACH.001

Data Populations

All patients who receive an Artegraft implant will be included in the safety and performance analyses for the device.

The early-access group is composed of the 50 patients that are enrolled, implanted with the Artegraft, successfully provided the first cannulation within 72 hours, and are followed to 6 months. This early-access population will be used to assess Primary, Assisted Primary, and Secondary Patency at 4, 12, and 26 weeks. This early-access population also will be used to assess perioperative major adverse clinical events (MACE) rates, and all adverse events to 26 weeks.

The late-access group is composed of 25 patients that are enrolled, implanted with the Artegraft, that are first accessed at >/= 10 days, and that are followed to 30 days post Day 0. This group will be used to assess perioperative major adverse clinical events (MACE) rates and primary, assisted primary, and secondary patency, at 30 days post Day 0. The late access group will also be assessed for patency at 6 months through a telephone interview or office visit to provide a more robust data set.

Table 1a: Schedule of Assessments (SoA) Early Access Patients

| Procedure | Screening Day -45 to Day of Surgery | Day 0 [1st successful cannulation] (May occur on day of surgery) | Day 1 – 17 Days post Day 0 | Day 30 +/- 3 days post Day 0 | 12 weeks +/- 7 days post day 0 | 6 Months +/- 7 days post day 0 | 12 Months +/- 14 days post day 0* Extended Follow-up |
|--|--|---|--|--|---|---|--|
| Eligibility (inclusion/exclusion) | Х | | | | | | |
| Informed Consent | Х | | | | | | |
| Medical History | Х | | | | | | |
| Prior and concomitant medication | Х | | Х | Х | Х | Х | |
| Physical Exam | Х | | Х | Х | Х | Х | |
| 12-Lead ECG, when medically indicated | X | | | | | | |
| Vessel mapping (if not done within 8 weeks) | Х | | | | | | |
| Pregnancy test: serum (Women of child-bearing potential only; to be assessed within 7 days of implant) | Х | | | | | | |
| Hematology and coagulation lab test | Х | | | | | | |
| Surgical implant of Artegraft | Х | | | | | | |
| Documentation of surgical procedure | X | | | | | | |
| Assessment of wound healing | | Х | Х | Х | Х | Х | |
| Graft Patency Assessment | Х | Х | Х | Х | Х | Х | Х |
| Adverse event assessment | Х | Х | Х | Х | Х | Х | X ⁺ |
| Medical Device malfunctions | Х | Х | Х | Х | Х | Х | |
| Documentation of graft interventions | X | Х | Х | Х | Х | Х | |
| Use of Dialysis Catheter | | Х | Х | Х | Х | Х | |

These patients will be having dialysis every few days – assessments should be the same or similar at each post-implant visit.

^{*} Extended follow-up will be assessed for patency and AEs only via a telephone follow-up or office visit

⁺ AEs between 6 months and 12 months.

Table 2b: Schedule of Assessments (SoA) Late Access and Early Access Drop-outs

| Procedure | Screening Day -45 to Day of Surgery | Day 0 [1st successful cannulation] (May occur on day of surgery) | Day 1 – 17 Days post Day 0 | Day 30 +/- 3 days post Day 0 | 6 Months +/- 7 days post day 0* Extended Duration Follow-up |
|--|--|---|----------------------------------|--|---|
| Eligibility (inclusion/exclusion) | Х | | | | |
| Informed Consent | Х | | | | |
| Medical History | Х | | | | |
| Prior and concomitant medication | Х | | Х | Х | |
| Physical Exam | Х | | X | Х | |
| 12-Lead ECG, when medically indicated | Х | | | | |
| Vessel mapping (if not done within 8 weeks) | Х | | | | |
| Pregnancy test: serum (Women of child-bearing potential only; to be assessed within 7 days of implant) | X | | | | |
| Hematology and coagulation lab test | Х | | | | |
| Surgical implant of Artegraft | Х | | | | |
| Documentation of surgical procedure | Х | | | | |
| Assessment of wound healing | | Х | Х | Х | |
| Graft Patency Assessment | Х | Х | Х | Х | Х |
| Adverse event assessment | Х | Х | Х | Х | X ⁺ |
| Medical Device malfunctions | Х | Х | Х | Х | |
| Documentation of graft interventions | Х | Х | Х | Х | |
| Use of Dialysis Catheter | | Х | Х | Х | |

These patients will be having dialysis every few days – assessments should be the same or similar at each post-implant visit.

^{**} Late access patients will be assessed for patency and AEs only via a telephone follow-up or office visit

⁺ AEs during time between 1 month and 6 months

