- Malas et al. 2017¹⁶ compared outcomes between BCA graft and ePTFE grafts for hemodialysis access in a single-institution retrospective review of 120 consecutive grafts placed in 98 patients between January 1, 2011, and June 30, 2014. Of the 120 grafts studied, 52 (43%) were BCA graft and 68 (57%) were ePTFE. Successful graft use for dialysis was 96% for BCA graft and 84% for ePTFE. Comparing BCA graft vs ePTFE, estimates for primary patency were 30% vs 43% at 1 year and 16% vs 29% at 2 years. Primary assisted patency was 36% vs 45% at 1 year and 24% vs 35% at 2 years. Secondary patency was 67% vs 48% at 1 year and 67% vs 38% at 2 years. There were no differences in primary and primary assisted for BCA graft compared with ePTFE. However, secondary patency was significantly higher for BCA graft compared with ePTFE, indicating better durability for the biologic graft than for ePTFE grafts in patients whose anatomy preclude placement of an arteriovenous fistula.
- Pineda et. al.³⁴ reported in 2017 the largest published experience with the current generation of BCA grafts for dialysis access and analyzed subgroups to determine the influence of obesity, gender, or prior access surgery on patency. This was a retrospective review of 134 BCA grafts implanted for hemodialysis access in the upper extremities of 126 patients between January 2012 and May 2015. For the entire group, 1-year primary patency was 32%, primary assisted patency was 49%, and secondary patency was 78%. Ten of 133 grafts (7%) developed infection requiring graft excision between 1 and 9 months after implantation. There was no statistical difference in primary or secondary patency for gender or body mass. Patients who had a BCA graft as their first access attempt had a higher primary and primary assisted patency than that of patients who had the graft placed after prior access failure. Primary patency of BCA grafts in this series was lower than that reported in a smaller randomized study, but primary assisted and secondary patency were similar.

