| Primary patency (%) | | | | | | |
| 3 months | 81 | 75 | 86 | | | |
| 6 months | 71 | 69 | 73 | | | |
| 1 year | 46 | 28 | 73 | | | |
| 1.5 years | 66 | 59 | 73 | | | |
| 2 years | 28 | 16 | 39 | | | |
| 3 years | 25 | 17 | 32 | | | |
| 4 years | 13 | 13 | 13 | | | |
| Primary assisted patency (%) | | | | | | |
| 3 months | 100 | 100 | 100 | | | |
| 6 months | 100 | 100 | 100 | | | |
| 1 year | 61 | 36 | 100 | | | |
| 1.5 years | 67 | 67 | 67 | | | |
| 2 years | 32 | 24 | 41 | | | |
| Secondary patency (%) | | | | | | |
| 3 months | 100 | 100 | 100 | | | |
| 6 months | 89 | 89 | 89 | | | |
| 1 year | 76 | 67 | 89 | | | |
| 1.5 years | 89 | 89 | 89 | | | |
| 2 years | 66 | 64 | 67 | | | |
| 3 years | 62 | 62 | 62 | | | |

Patency Definition from SVS Reporting Standards³¹ are given below and should be used in evaluation of patency.

Artegraft, Inc.
Protocol: ARTCT.BEACH.001

Primary patency. This is the interval from the time of access placement until any intervention designed to maintain or reestablish patency, access thrombosis, or the time of measurement of patency.

Assisted primary patency. This is the interval from the time of access placement until access thrombosis or the time of measurement of patency, including intervening manipulations (surgical or endovascular interventions) designed to *maintain* the functionality of a patent access (number of interventions can be represented numerically in between brackets after the actual patency of an access; i.e., assisted primary patency of 18 months [2]. This indicates that the access has been functional for 18 months but needed two interventions to maintain its functionality).

Secondary patency. This is the interval from the time of access placement until access abandonment, thrombosis, or the time of patency measurement including intervening manipulations (surgical or endovascular interventions) designed to *reestablish* functionality in thrombosed access.

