9.0 STATISTICAL PLAN

9.1 Sample Size Determination

The sample size for this study is logistically rather than statistically driven.

A total of 50 patients will be enrolled, randomized and successfully provided early cannulation within 72 hours, and followed to 6 months. Another group of 25 patients will be randomly assigned and provided cannulation for 10 or more days after implant and followed only to 30 days to assess perioperative MACE rates. No loss to follow-up is projected at 30-days post implantation.

Previously published patency data (refer to the background section above) will be used at 12 weeks and 6 months for clinical context. The early access study group results will be compared with these previously published data, which were reported for Artegraft normal cannulation times. It should be noted that complications may or may not result in an early access failure. Confidence intervals will be presented around each endpoint. The observed rates will be numerically compared with the expected rates and no formal statistical hypothesis will be tested.

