9.2.8 Effectiveness

The effectiveness analysis population will include a subset of the ITT analysis population who are implanted with the Artegraft based on the randomized early or late vascular access with the applicable

Artegraft, Inc. Version 4.0 21June2019
Protocol: ARTCT.BEACH.001 CONFIDENTIAL Page 45 of 81

performance/effectiveness responses reported for each randomized group. The effectiveness analysis population will be used in reporting the performance /effectiveness of the randomized early or late vascular access groups.

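### The synopsis builds the patency groups from grafts that reached first cannulation, although patency runs from placement; grafts lost before first use drop out, and other sections contradict this denominator.

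*Combined protocol and SAP*

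**What the plan says.** The Protocol Summary (1.0, Data Populations) defines the early group as 50 patients who were enrolled, implanted, "successfully provided the first cannulation within 72 hours, and are followed to 6 months". It then assigns the patency analyses to that group: "This early-access population will be used to assess Primary, Assisted Primary, and Secondary Patency at 4, 12, and 26 weeks". The late group is 25 implanted patients "that are first accessed at >/= 10 days, and that are followed to 30 days post Day 0", and it is used for 30-day patency. Section 6.0 replaces early patients who miss the 72-hour window until 50 is reached.

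The patency clock starts earlier than either condition. Section 3.2 adopts the SVS definitions; for secondary patency: "This is the interval from the time of access placement until access abandonment, thrombosis, or the time of patency measurement". Section 4.0 times the 12-week and 6-month results in the early group from implantation.

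Other text points to a wider denominator. The Data Populations block opens with: "All patients who receive an Artegraft implant will be included in the safety and performance analyses for the device". Section 9.2.6 analyses randomised patients as assigned, whatever access time they received, if any. Section 9.2.8 states: "The effectiveness analysis population will include a subset of the ITT analysis population who are implanted with the Artegraft", with responses reported for each randomised group.

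On the comparison, Section 9.1 says: "The early access study group results will be compared with these previously published data". The published rates are used at 12 weeks and 6 months, numerically and without a hypothesis test.

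**The concern.** If the clock starts at placement but a graft is admitted only once it has been cannulated, the time before first use is free of failure by construction. Grafts lost in that period leave the numerator and the denominator together, so the reported rate can only rise.

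The required survival also differs by arm: up to 72 hours for an early graft, at least 10 days for a late one. Section 4.0 expects similar 30-day patency in the two groups, and that comparison would be made between differently selected grafts.

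Two readings of the denominator also stand side by side in an open-label trial. Unless the choice is fixed in advance, it can be made after outcomes are known.

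**Working it through.** **Which text governs the denominator**

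- The Data Populations block is the only place that names the patency population, and it conditions on achieved cannulation.
- Its opening sentence includes every implanted patient in the performance analyses.
- Section 9.2.6 would keep all randomised patients, but Table 8 in Section 9.2.4 marks the ITT population for baseline and disposition only.
- Section 9.2.8 does not require cannulation, but it does require a reported response. In Tables 1a and 2b the scheduled visits after surgery run from Day 0, the first successful cannulation. A graft that is never cannulated has no Day 0, so no post-surgical visit is scheduled to produce a response.

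The wider wording therefore contradicts the narrower wording without securing that pre-use losses are counted.

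**The plan's own figures**

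The 50 + 25 sample size is described as logistical, so there is no calculation to reproduce. The published mean primary patency rates in Section 3.2 are the midpoints of their ranges: (69 + 73)/2 = 71 at 6 months, and (75 + 86)/2 = 80.5, shown as 81, at 3 months.

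**Size of the bias**

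Let S be patency among all implanted grafts and f the share lost before first use. Among cannulated grafts the rate is S/(1 − f). The documents give no f for this trial; 1% to 4% is assumed. The 4% end is 100% − 96%, from one cited retrospective series: "Successful graft use for dialysis was 96% for BCA graft and 84% for ePTFE".

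| All-implant rate S | f = 1% | f = 2% | f = 4% |
|---|---|---|---|
| 6-month primary, 71% (published mean) | 71.7% | 72.4% | 74.0% |
| 6-month primary, 65% (expected) | 65.7% | 66.3% | 67.7% |
| 3-month primary, 75% (expected) | 75.8% | 76.5% | 78.1% |
| 30-day primary, 85% (expected) | 85.9% | 86.7% | 88.5% |

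For example, 71/0.99 = 71.7 and 71/0.96 = 74.0.

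**Uneven conditioning**

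Suppose both arms have an all-implant 30-day rate of 85%, with f = 1% in the early arm and 4% in the late arm. The reported rates would be 85/0.99 = 85.9% and 85/0.96 = 88.5%, a gap of just under 3 points in favour of late access with no true difference. These two values of f are assumptions.

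**Precision**

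With 36 of 50 patent (72%), the Clopper-Pearson 95% interval is 57.5% to 83.8%, about ±14 points. A shift of 1 to 3 points is small beside this, but it is systematic.

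**Patients who miss the window**

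The plan expects up to 10. Suppose the 50 analysed have 65% patency and x of the 10 lost the graft before use, with the rest also at 65%. The rate over all 60 is 0.65 × (60 − x)/60:

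- x = 0: 65.0%
- x = 1: 63.9%
- x = 2: 62.8%
- x = 5: 59.6%
- x = 10: 54.2%

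The last value is an extreme, since many who miss the window may simply be cannulated later.

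**The case against.** Section 9 can be read as already correct: patency is an effectiveness endpoint, Table 8 assigns effectiveness to the Effectiveness population, and Section 9.2.8 does not require cannulation. This stands to the extent that the exclusion is not settled; it is an unresolved contradiction. It does not remove the problem, because the synopsis states the opposite and a never-cannulated graft has no scheduled response.

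A reader might also infer that the trial's patency is inflated against its published benchmark because the published rates count every implant. The documents do not support that as a fact:

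- They do not give the sources or denominators of the 3- and 6-month rates.
- The patency table in Section 3.2 reports 100% assisted primary patency at 3 and 6 months and 100% secondary patency at 3 months. A 4% pre-use loss counted as failure would cap these at 96%.
- The series with 96% use is quoted for patency at 1 and 2 years only, and at least one other cited series reports by cannulation cohort.
- Section 9.1 compares only the early group with published data, so the late group has no such benchmark.

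A further temptation is to treat the Section 4.0 expectations as pass marks. With 50 patients and a true all-implant secondary patency of 90%, the chance of seeing at least 45 patent is 62%. It would be 91% if the rate were 0.90/0.96, but 70% if it were 0.90/0.99. The larger figure applies the whole never-used share of another series to a wait of at most 72 hours, and that series does not say its unused grafts had failed. The plan also sets no pass mark.

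**Conclusion.** The point holds in this form: as the synopsis is written, the patency groups are selected on reaching first cannulation while the clock starts at placement, and the documents contradict themselves on the denominator. The direction is upward in both arms. The selection is potentially stronger in the late arm, which affects the 30-day comparison.

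The size is unknown. Under an assumed pre-use loss of 1% to 4%, with those losses counted as failures, a 6-month primary rate of 71% would read about 72% to 74%. Loss within 72 hours in the early arm may lie at the low end. The effect is modest against the interval width unless several of the patients who miss the window have lost their grafts. Inflation relative to the published rates would be a further assumption and is not part of this conclusion. No error rate or power is affected, because no hypothesis is tested.

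**What to change.** In the Data Populations block and Section 9.2.3, state one rule:

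- Patency is estimated by Kaplan-Meier from implantation in all randomised patients, by randomised group. Under Section 7.6, randomisation follows successful implantation, so all of them are implanted.
- Thrombosis or abandonment before first cannulation is a failure on that date.
- Early patients who miss the window are censored at their last documented patency and intervention assessment.
- Results in the groups defined by achieved cannulation are supportive.

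Align Section 9.2.8 and Table 8 with this rule. In Section 9.1, use the all-randomised early-arm curve for the comparison with published rates, and state that the denominators of those rates are not known.

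The cost is more than wording. Table 2b runs from Day 0, has no 12-week visit and stops recording graft interventions at Day 30. Never-cannulated grafts therefore need one graft-status record dated from implantation, and early patients who miss the window will be censored earlier for primary patency. The reported rates may be slightly less favourable.
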